13.2.2 Analysis Populations

The following analysis populations will be defined for the statistical analyses:

- The Safety population will include all randomized patients who received at least 1 dose of the study product.
- The mITT population will include all randomized patients who met all inclusion/exclusion criteria, received at least 1 dose of the study drug and recorded the number of formed and unformed bowel movements during Study Day 1.
- The PP population will include all randomized patients from the mITT population who do not have a major protocol deviation that would affect treatment evaluation. Patients who discontinue the study due to lack of treatment effect after completing 3 days of treatment or whose condition worsens and who require alternate or supplemental therapy for the treatment of TD should be included in the PP population (see Section 13.2.5 for the handling of missing values).

Major protocol deviations include but are not limited to:

- lack of compliance defined as having administered <75% or >125% of the scheduled doses for the specified duration of the study
- completion of the TOC/EOS Visit outside the specified visit window (Study Day 5 \pm 1 day) (if patient did not discontinue the study due to lack of treatment effect or worsening of the underlying condition requiring alternate or supplemental therapy).

Further major protocol deviations will be defined in the SAP.

The PP population will be the primary population for establishing equivalence of rifaximin and Xifaxan regarding the primary efficacy endpoint (clinical cure). The mITT population will be the primary population for evaluation of the study sensitivity comparing the proportions of clinical cure between rifaximin and placebo and Xifaxan and placebo.

13.2.3 Primary Endpoint Analysis

The primary endpoint is clinical cure at the TOC/EOS Visit (Study Day 5 ± 1 day). Clinical cure is defined as either:

- No stools or only formed stools within a 48 hour period and no fever, with or without other enteric symptoms, OR
- No watery stools or no more than two soft stools passed within a 24 hour period with no fever and no other enteric symptoms except for mild excess gas/flatulence.

Patients will assess stool consistency and document it in the patient's diary; stools will be classified, as formed (retains shape), soft (assumes the shape of container), or watery (can be poured). When using this classification, both soft and watery stools are unformed and abnormal.

Therapeutic equivalence will be concluded if the 90% CI of the difference of the success proportions between rifaximin and Xifaxan is completely contained within the interval $[-0.20; 0.20]$. This approach can be alternatively formulated as a statistical test problem where the compound hypothesis to be tested is:

$$H_0: p_G - p_R < -0.20 \text{ or } p_G - p_R > 0.20$$

against the alternative

$$H_1: -0.20 \leq p_G - p_R \leq 0.20.$$

Here p_G denotes the probability of clinical cure at the TOC/EOS Visit for rifaximin and p_R denotes the respective probability for Xifaxan.

Two one-sided Z tests at the 0.05 significance level will be used for the above test problem. The PP population will be the primary analysis set for the assessment of therapeutic equivalence.

Study sensitivity will be evaluated by comparing the success proportions between rifaximin and placebo and Xifaxan and placebo. Two two-sided Z tests with pooled variance will be used. The significance level of each of these tests will be set to 0.05. The mITT population will be the primary analysis set for assessing study sensitivity.

The primary endpoint will also be analyzed by subgroups according to the pathogen status at baseline:

- inflammatory/invasive pathogens (i.e. *Campylobacter jejuni*, *Shigella* species, and *Salmonella* species)
- diarrheagenic *E Coli* group without evidence of inflammatory/invasive pathogens
- Other pathogens without evidence of inflammatory/invasive pathogens.

All p-values resulting from these subgroup analyses will be interpreted in the exploratory sense.

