- microbiological cure rate defined as a post-treatment culture that was negative for the pre-treatment etiologic pathogen.

Safety endpoints:

- Incidence of reported AEs
- Changes in vital signs and clinical laboratory parameters.

Pharmacokinetics: There is no pharmacokinetic evaluation planned in this study.

Statistical Methods:

Sample size and power:

A sample size of 135 in the generic rifaximin and 135 in the reference listed drug (RLD) Xifaxan treatment groups achieve approximately [REDACTED] power to detect therapeutic equivalence when the margin of equivalence, given in terms of the difference, extends from -0.20 to 0.20.

Concerning the assessment of study sensitivity, a sample size of 170 in the generic rifaximin group and RLD Xifaxan[®] group and 85 in the placebo group achieve approximately [REDACTED] power to detect a difference between the group proportions of [REDACTED]

Patients will be randomized 2:2:1 to generic rifaximin (n=180), Xifaxan (n=180), and placebo (n=90). A total of 450 patients will be randomized. As it can be anticipated that no more than 5% of patients will be excluded from the modified Intent to Treat (mITT) population, and no more than 20% of patients from the mITT population will be excluded from the PP population this sample size will have sufficient power to show therapeutic equivalence and study sensitivity.

Efficacy:

The primary endpoint will be clinical cure at the TOC/EOS Visit (Study Day 5 ± 1 day). Equivalence will be concluded if the 90% confidence interval of the difference of the success proportions between rifaximin and Xifaxan is completely contained within the interval [-0.20; 0.20]. Two, one-sided Z tests at the 5% significance level will be used. The PP population will be the primary analysis set.

Study sensitivity will be evaluated by comparing the success proportions between rifaximin and placebo and Xifaxan and placebo. The two-sided Z test with pooled variance will be used. The significance level of the test is 0.05. The mITT population will be the primary analysis set.

The primary endpoint will also be analyzed by subgroups according to the pathogen status at baseline.

Secondary efficacy variables

The analysis of all secondary endpoints will be performed in the mITT and PP populations.

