9.2 Discussion of Study Design

The study was designed following the guidance published by the Food and Drug Administration's (FDA) Office of Generic Drugs (OGD)¹¹. The guidance requires a randomized, double blind, parallel, placebo controlled study in male and non-pregnant female patients with TD to demonstrate the therapeutic equivalence of rifaximin 200 mg tablets to Xifaxan 200 mg tablets. All the main design features of the study are in accordance with the OGD guidance (e.g. study population, efficacy endpoints, the controls used [Xifaxan and placebo] and statistical methodology).

The equivalence margin for the primary endpoint was recommended by the OGD guidance (the 90% confidence interval [CI] of the test - reference difference between products for the primary endpoint has to be contained within [-0.20, +0.20] using the per protocol [PP] population). A placebo control arm was included to demonstrate that rifaximin and Xifaxan are active, and to establish that the study is sufficiently sensitive to detect differences between products.

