9.2.1 Risk/Benefit and Ethical Assessment

Rifaximin is already approved by the FDA for use in the treatment of TD at the posology used in the present study.

The risks associated with the treatment are well established and considered acceptable (see Xifaxan full prescribing information in Appendix I). In two placebo controlled trials comparing Xifaxan 200 mg three times daily (n=320) with placebo (n=228), discontinuations due to adverse reactions occurred in only 0.4% of patients (events of taste loss, dysentery, weight decrease, anorexia, nausea and nasal passage irritation). Of the adverse reactions that occurred at a frequency >2% in Xifaxan-treated patients, headache was the only event which occurred at a higher rate with Xifaxan (10%) than placebo (9%).

As TD normally spontaneously resolves without treatments after approximately 4 days⁵, including a placebo arm (as recommended by the OGD) is considered to be ethically acceptable. The 2:2:1 randomization ensures that the maximum number of patients receive active treatment. In addition, patients will receive a phone call on Study Day 3 to identify patients who may need to receive an alternative or supplemental therapy.

There are no adequate and well-controlled studies in pregnant women, however pregnant or lactating women will not be enrolled in this study. There is no information regarding the presence of rifaximin in human milk, the effects of rifaximin on the breastfed infant, or the effects of rifaximin on milk production. Any pregnancy that occurs during the study must be handled as described in Section 12.1.6.

The safety and effectiveness of rifaximin has not been established in pediatric patients less than 12 years of age with TD. Patients less than 18 years of age will not be enrolled in this study.

Because this study will enroll tourists who will not be local to the study facility, the Investigator will ensure that the prospective patient is able to understand the language of the study (Section 17.3) and is able to understand instructions for, and adequately complete, specified study activities (Section 18.2), prior to enrollment in the study.

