13 STATISTICAL EVALUATION

13.1 Sample Size and Power

According to the FDA Draft Guidance on rifaximin¹¹ sample sizes should be chosen such that the power is sufficient to establish therapeutic equivalence between generic and RLD rifaximin (Xifaxan) and sufficient to show that both are active compared to placebo (study sensitivity). Therapeutic equivalence is to be shown for the PP population whereas study sensitivity is to be shown for the modified Intent-to-Treat (mITT) population (Section 13.2.2).

A sample size of 135 in the generic rifaximin and 135 in the Xifaxan treatment groups achieve approximately [REDACTED] power to detect therapeutic equivalence when the margin of equivalence, given in terms of the difference, extends from -0.20 to 0.20. The calculations assume that:

- two one-sided Z tests (pooled) at the 0.05 significance level are used (corresponding to a 90% CI for the difference of success proportions);
- [REDACTED]
- [REDACTED]

Concerning the assessment of study sensitivity, a sample size of 170 in the rifaximin group, 170 in the Xifaxan group and 85 in the placebo group achieve approximately [REDACTED] power to detect a difference between the group proportions of [REDACTED], assuming that:

- [REDACTED]
- two-sided Z tests (pooled) at the 0.05 level will be used.

Patients will be randomized 2:2:1 to rifaximin (n=180), Xifaxan (n=180), and placebo (n=90). A total of 450 patients will be enrolled. As it can be anticipated that no more than 5% of patients will be excluded from the mITT population and no more than 20% of patients will be excluded from the PP population¹² this sample size will have sufficient power to show therapeutic equivalence and study sensitivity.

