14 CLINICAL STUDIES

14.1 Travelers' Diarrhea

The efficacy of XIFAXAN given as 200 mg orally taken three times a day for 3 days was evaluated in 2 randomized, multi-center, double-blind, placebo-controlled studies in adult subjects with travelers' diarrhea. One study was conducted at clinical sites in Mexico, Guatemala, and Kenya (Study 1). The other study was conducted in Mexico, Guatemala, Peru, and India (Study 2). Stool specimens were collected before treatment and 1 to 3 days following the end of treatment to identify enteric pathogens. The predominant pathogen in both studies was *Escherichia coli*.

The clinical efficacy of XIFAXAN was assessed by the time to return to normal, formed stools and resolution of symptoms. The primary efficacy endpoint was time to last unformed stool (TLUS) which was defined as the time to the last unformed stool passed, after which clinical cure was declared. Table 4 displays the median TLUS and the number of patients who achieved clinical cure for the intent to treat (ITT) population of Study 1. The duration of diarrhea was significantly shorter in patients treated with XIFAXAN than in the placebo group. More patients treated with XIFAXAN were classified as clinical cures than were those in the placebo group.

Table 4. Clinical Response in Study 1 (ITT population)

	XIFAXAN (n=125)	Placebo (n=129)	Estimate (97.5% CI)
Median TLUS (hours)	32.5	58.6	2 ¹ (1.26, 2.50)
Clinical cure, n (%)	99 (79)	78 (60)	19 ² (5.3, 32.1)

1. Hazard Ratio (p-value <0.001)

2. Difference in rates (p-value <0.01)

Microbiological eradication (defined as the absence of a baseline pathogen in culture of stool after 72 hours of therapy) rates for Study 1 are presented in Table 5 for patients with any pathogen at baseline and for the subset of patients with *Escherichia coli* at baseline. *Escherichia coli* was the only pathogen with sufficient numbers to allow comparisons between treatment groups.

Even though XIFAXAN had microbiologic activity similar to placebo, it demonstrated a clinically significant reduction in duration of diarrhea and a higher clinical cure rate than placebo. Therefore, patients should be managed based on clinical response to therapy rather than microbiologic response.

Table 5. Microbiologic Eradication Rates in Study 1 Subjects with a Baseline Pathogen

	XIFAXAN	Placebo
Overall	48/70 (69)	41/61 (67)
E. coli	38/53 (72)	40/54 (74)

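### The protocol's rule concludes therapeutic equivalence from the rifaximin–Xifaxan interval alone; beating placebo is intended but is not a condition

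*Protocol*

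**What the plan says.** Section 13.2.3 of the protocol gives the decision rule: "Therapeutic equivalence will be concluded if the 90% CI of the difference of the success proportions between rifaximin and Xifaxan is completely contained within" the margin of -0.20 to 0.20. The null and alternative hypotheses that follow involve only the cure probabilities of rifaximin and Xifaxan, and PP is the primary analysis set. The synopsis has the same rule: "Equivalence will be concluded if the 90% confidence interval of the difference of the success proportions between rifaximin and Xifaxan is completely contained within" that margin.

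The placebo comparisons come afterwards in 13.2.3 as a separate item: "Study sensitivity will be evaluated by comparing the success proportions between rifaximin and placebo and Xifaxan and placebo". They use two-sided pooled Z tests at 0.05 each in the mITT population. Neither 13.2.3 nor the synopsis says what result counts as success, in which direction, or what follows from failure.

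The purpose is stated elsewhere. Section 9.2 says the placebo arm is there to show that both products are active and "to establish that the study is sufficiently sensitive to detect differences between products". Section 13.1 asks for power "sufficient to show that both are active compared to placebo (study sensitivity") and says that "study sensitivity is to be shown for the modified Intent-to-Treat (mITT) population". Section 8.1 lists the placebo comparison as an addition to the primary objective, and 13.2.2 assigns the analysis populations. None of these ties the placebo tests to the equivalence conclusion. The SAP repeats the objectives and the sample-size text without adding a decision rule. Its sections 1 and 9 limit the final analysis to safety because few patients were randomized.

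**The concern.** An equivalence interval cannot tell two products that work equally well from two products that work equally little. The placebo arm is meant to separate these cases, and it can do so only if its result enters the conclusion. As written, a trial that failed both placebo tests would still meet the stated criterion.

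The protocol makes an insensitive trial a realistic possibility. Section 9.2.1 says: "As TD normally spontaneously resolves without treatments after approximately 4 days". The test of cure is on Study Day 5 (± 1 day), after that time for many patients. The label study in Appendix I, section 14.1, had 60% cure on placebo. Section 7.2 allows treatment before a pathogen is confirmed, while Appendix I, section 5.1, reports no demonstrated effectiveness against pathogens other than *E. coli*.

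Direction is a smaller part of the point. The tests are two-sided, and 13.2.3 does not say that a significant difference must favour the active product.

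**Working it through.** **Inputs from the plan.** Randomization 180/180/90; margin ±0.20 with a 90% CI; placebo tests two-sided at 0.05 with pooled variance. Evaluable numbers in 13.1: 135 per active arm (PP) and 170/170/85 (mITT).

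**The plan's own figures.** 180 × 0.95 = 171 (stated 170); 90 × 0.95 = 85.5 (stated 85); 171 × 0.80 = 136.8 (stated 135). These reproduce. The stated powers and planning rates are redacted and cannot be checked.

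**Assumptions.** All cure rates below are assumed. The 79% and 60% come from the label study in Appendix I, section 14.1 (99/125 and 78/129); the others show a range. PP patients are a subset of mITT, with the same cure rate in both.

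**CI rule when all arms have the same cure rate p.** With n = 135 per arm and no true difference,

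Pr(conclude) ≈ 2Φ(0.20/SE − 1.645) − 1, where SE = √(2p(1−p)/135).

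At p = 0.60: SE = √(0.48/135) = 0.0596; 0.20/0.0596 − 1.645 = 1.709; the probability is 0.913. The exact binomial calculation with the unpooled interval gives 0.911. Pooling the variance changes the exact figures by at most 0.002.

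**Joint rule.** Simulation with 2,000,000 trials per scenario. Because the placebo arm is shared, the two placebo tests are correlated: (1/85)/(1/170 + 1/85) = 2/3. Their joint probability is therefore not the product of the single ones.

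| Common cure rate, all arms | CI rule (exact) | CI rule and both products significantly better than placebo |
|---|---|---|
| 50% | 90.0% | 0.7% |
| 60% | 91.1% | 0.8% |
| 70% | 94.8% | 0.8% |
| 80% | 98.6% | 0.8% |

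**Direction.** At 60% in all arms, requiring significance without direction gives 1.5%; about half of that (0.7%) has both products significantly worse than placebo. If both products are truly worse (50% against 60%), the CI rule with undirected significance passes in about 19% of trials and the directed rule in practically none.

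**Inert generic, working Xifaxan** (60% against 79%, placebo 60%). The CI rule passes in 7.0% of trials and the joint rule in 0.7%. The interval alone largely handles this case.

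**Cost when both products work.** For one placebo test at 79% against 60%: pooled proportion (170 × 0.79 + 85 × 0.60)/255 = 0.727; null SE 0.0592; alternative SE 0.0616; power Φ((0.19 − 1.96 × 0.0592)/0.0616) = Φ(1.20) = 0.885. Simulation gives 0.887.

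| Rifaximin/Xifaxan/placebo | CI rule | Each placebo test | Both placebo tests | Joint rule |
|---|---|---|---|---|
| 79/79/60 | 98.3% | 88.7% | 82.6% | 81.7% |
| 75/75/60 | 96.9% | 68.8% | 57.1% | 56.2% |
| 70/70/60 | 94.8% | 36.3% | 23.7% | 23.2% |

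The joint figure is within one percentage point of the chance of winning both placebo tests. The difference between the CI rule and the joint rule is the share of trials in which the written rule concludes equivalence although at least one placebo test failed: 98.3 − 81.7 = 16.6% at the label rates, and 94.8 − 23.2 = 71.6% at 70/70/60.

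**The case against.** The strongest reply is that this trial will draw no equivalence conclusion at all, because SAP v1.0 drops efficacy and section 8.6 of the SAP rules out statistical tests. That is correct, and it limits the practical effect to reuse of the protocol's rule or to any efficacy result reported under it.

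The second reply is that the substance is already there. Sections 9.2 and 13.1 say that both products are to be shown active, which can sensibly mean only better than placebo, and a failed sensitivity test would be visible beside the equivalence result. The intent is clear, and it weakens the complaint about direction: two-sided tests at 0.05 are a normal way to test superiority. But 13.2.3 is where the protocol says what will be concluded, and a rationale in another section does not change that criterion.

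Third, the 90–99% figures suppose that neither product works, and no probability is attached to that. The label points the other way: "More patients treated with XIFAXAN were classified as clinical cures than were those in the placebo group". A high placebo cure rate makes low sensitivity plausible, not inactivity. This is fair. The figures show how the rule behaves in that case, not how likely the case is. Finally, 9.2 says the methodology follows the regulator's draft guidance. That document is not available here, so whether it already covers a failed sensitivity test is unknown.

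**Conclusion.** The concern holds. The written criterion depends only on the rifaximin–Xifaxan interval, and no section of the protocol or SAP makes success against placebo a condition of concluding equivalence. When all arms share a cure rate between 50% and 80%, the rule concludes equivalence in 90.0% to 98.6% of trials, against 0.7–0.8% under a joint, directed rule. The main exposure is an insensitive trial; an inert generic against a working reference passes the interval rule in only 7.0% of trials at the assumed rates.

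The figures rest on assumed cure rates, the plan's evaluable numbers, and equal cure rates in PP and mITT. The textual finding rests on none of these. It is a point that should be corrected in the protocol's rule, with no bearing on the safety-only analysis under SAP v1.0.

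**What to change.** In 13.2.3 and in the synopsis, replace the criterion with a joint one, for example: *Equivalence is declared only when (a) the PP 90% CI for rifaximin minus Xifaxan lies inside [-0.20; 0.20], and (b) rifaximin and Xifaxan each show a significantly higher cure proportion than placebo in the mITT population, each test two-sided at 0.05.* No alpha adjustment is needed, because every condition must be met.

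In 13.1, add the power of this joint rule at the planning rates, next to the two separate power statements.

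The change needs no further data. It lowers the stated chance of success: from 98.3% to 81.7% at 79/79/60, from 96.9% to 56.2% at 75/75/60, and from 94.8% to 23.2% at 70/70/60. In these scenarios both products truly work, so the loss is failure to show sensitivity, not prevention of a false claim. Nearly all of it is the existing risk of missing one of the two placebo tests, which the separate power statements do not show. Whether 450 patients give adequate joint power is for the sponsor to check against the redacted planning rates.

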13.2.4 Secondary Endpoint Analysis

The analysis of all secondary endpoints will be performed in the mITT and PP populations.

13.2.4.1 Time to Last Unformed Stool

TLUS is defined as the interval beginning with the first dose of study drug and ending with the last unformed stool passed.

TLUS will be calculated for each patient in the following manner:

Step 1: Identify when the patient achieves clinical cure (definition see Section 13.2.3).

Step 2: Moving backwards from this time, identify the time of the last unformed stool.

Step 3: The TLUS equals the time from the first dose of study drug to the time of the last unformed stool identified in Step 2.

Patients who met the criteria for clinical cure (Section 13.2.3) immediately after the start of study drug and prior to passing any unformed stools will be defined as having a TLUS of 0 hours. Patients for whom TLUS cannot be calculated because they terminated early due to clinical failure (Section 13.2.4.2) will have censored TLUS of 120 hours. Patients who terminate early due to reasons other than clinical failure (AE, patient request, intercurrent illness) or because they completed the study without achieving clinical cure will have censored TLUS at the time of the last available information on unformed stools.

Rifaximin will be compared to Xifaxan, and the rifaximin groups to placebo using a Cox proportional hazards model with treatment group and center as independent variables. A treatment by center term will also be included to assess potential treatment by center interactions. Centers with 5 or fewer patients per treatment arm will be pooled with geographically related centers to form analysis centers.

